## 2.3 Safety objectives

Safety Objective	Outcome Measures
To evaluate the safety and tolerability of anifrolumab	Adverse events (including AESIs), vital signs, physical examination, 12 lead ECG, clinical laboratory tests (haematology, clinical chemistry, urinalysis), C-SSRS

## 2.4 Exploratory objectives

Exploratory Objectives	Endpoints/Outcome Measures
To explore the difference between anifrolumab and placebo on measures of disease activity including levels [REDACTED]	[REDACTED]
[REDACTED]	[REDACTED]
[REDACTED]	[REDACTED]
[REDACTED]	[REDACTED]
[REDACTED]	[REDACTED]
To explore the difference between anifrolumab and placebo on [REDACTED]	[REDACTED]
[REDACTED]	[REDACTED]

To explore the difference between anifrolumab and placebo on [REDACTED]

Note: Estimand descriptions for the key/other secondary endpoints are detailed fully in the SAP.

a: Restricted medication is described in Section 7.7. There may be some special cases of RM use intercurrent events where participants are eligible to respond after some duration of time. Additional details are given in the SAP.

ADA = Anti-drug antibody; BICLA = British Isles Lupus Assessment Group-based Composite Lupus Assessment; C3 = Third component of complement; C4 = Fourth component of complement; CLASI = Cutaneous Lupus Erythematosus Disease Area and Severity Index; dsDNA = double stranded deoxyribonucleic acid; ECG = Electrocardiogram; EQ-5D-5L = EuroQoL 5 dimensions; LLDAS = Lupus Low Disease Activity State; OCS = oral corticosteroids; PGA = Physician's Global Assessment; PK = Pharmacokinetic(s); SDI = Systemic Lupus International Collaborating Clinics/American College of Rheumatology Damage Index; SLEDAI-2K = Systemic Lupus Erythematosus Disease Activity Index 2000; SRI(4) = Systemic Lupus Erythematosus Responder Index of  $\geq 4$ ; VAS = Visual analogue scale.

### **3 PARTICIPANT SELECTION, ENROLMENT, RANDOMISATION, RESTRICTIONS, DISCONTINUATION AND WITHDRAWAL**

Prospective approval of protocol deviations to recruitment and enrolment criteria, also known as protocol waivers or exemptions, is not permitted.

#### **3.1 Inclusion criteria**

Participants are eligible to be included in the study only if all of the following criteria apply:

##### **Informed Consent**

1. Capable of giving signed informed consent as described in [Appendix A](#) which includes compliance with the requirements and restrictions listed in the ICF and in this protocol.
2. Written informed consent and any locally required authorization (if applicable) obtained from the participant prior to performing any protocol-related procedures, including Screening evaluations.
3. In the opinion of Investigator, must be able to comprehend the ICF and all protocol related assessments, such that the participant can complete all study required documents, procedures, and outcome measures.
4. Completion of Screening procedures within 35 days after signing the ICF.

##### **Age**

5. Participant must be 18 to 70 years of age inclusive, at the time of signing the ICF.

##### **Disease Characteristics**

6. Participants who have a diagnosis of paediatric or adult SLE according to the ACR 1997 revised criteria ([Stoll et al, 2004](#); [Tan et al, 1982](#); see [Appendix D](#)) for  $\geq 24$  weeks prior to signing the ICF.
7. Must be receiving at least one of the following standard therapy regimens at Screening:
  - (a) Oral prednisone (or equivalent) monotherapy:
    - Start date: minimum daily dose:  $\geq 7.5$  mg/day for at least 8 weeks prior to Day 1 (randomisation)
    - Must be stable for  $> 2$  weeks before Day 1 (randomisation)
    - Maximum daily dose:  $\leq 40$  mg/day
  - (b) Antimalarials and/or immunosuppressant(s) with or without OCS:
    - Permitted medications include: antimalarials, azathioprine, mycophenolate mofetil/mycophenolic acid, methotrexate, mizoribine, tacrolimus, and cyclosporine (Note: The combination of azathioprine and methotrexate is not allowed due to known safety issues. The combinations of tacrolimus/cyclosporine

with other immunosuppressants above should be avoided. Combination with antimalarials is allowed.)

- Start date:  $\geq 12$  weeks prior to signing the ICF.
- Must be stable  $\geq 8$  weeks prior to signing the ICF.
- The daily dose should follow the local medical practice and not exceed the maximum allowed daily dose:
  - Azathioprine:  $\leq 200$  mg/day.
  - Mycophenolate mofetil  $\leq 2$  g/day or mycophenolic acid  $\leq 1.44$  g/day.
  - Oral, subcutaneous (SC), or intramuscular methotrexate  $\leq 25$  mg/week.
  - Mizoribine  $\leq 150$  mg/day.
  - Tacrolimus  $\leq 0.2$  mg/kg/day or cyclosporine  $\leq 5$  mg/kg/day, monitoring of serum concentration may be performed at the discretion of Investigator where local practice guidelines mandate or in case of safety concerns.

(c) Oral prednisone (or equivalent) plus immunosuppressant(s):

- Start dates for OCS and immunosuppressants must be met.
- Stability requirements for each medication must be met.
- No minimum daily dose for OCS when in combination with immunosuppressants.
- Maximum daily dosages for each medication in (a) and (b) must not be exceeded.

8. Autoantibody-positive at Screening, as determined by the central laboratory, for at least one of the following:

- (a) Antinuclear antibody (ANA) immunofluorescent assay test (titer  $\geq 1:80$ ).
- (b) Anti-dsDNA.
- (c) Anti-Smith (anti-Sm).

9. To be eligible a participant must have SLEDAI-2K  $\geq 6$  points, with  $\geq 4$  points coming from clinical components ("Clinical" SLEDAI-2K) at screening.

In addition, the following criteria for "Clinical" SLEDAI-2K must be met:

- (a) Clinical SLEDAI of at least  $\geq 4$  points at Day 1 (randomization).

Note: The "Clinical" SLEDAI-2K is the SLEDAI-2K assessment score without the inclusion of points attributable to any urine or laboratory results including immunologic measures:

- Includes points from the following clinical components: arthritis, myositis, rash, alopecia, mucosal ulcers, pleurisy, pericarditis, or vasculitis.
- Excludes points attributed to a fever, an SLE headache, and organic brain syndrome.

- (b) In order to qualify for SLEDAI-2K score for arthritis at screening, participant must have at least 3 joints with tenderness AND swelling (same joints) due to SLE.
  - (c) In order to qualify for SLEDAI-2K score for rash at screening, participant must have rash with significant erythema (not only faint pink erythema).
  - (d) Clinical SLEDAI-2K points at screening cannot only be due to alopecia and mucosal ulcers.
10. At screening, BILAG-2004 ([Appendix F](#)) with at least 1 of the following:
- (a) BILAG-2004 level A disease in  $\geq 1$  organ system.
  - (b) BILAG-2004 level B disease in  $\geq 2$  organ systems.
11. PGA score  $\geq 1.0$  on a 0 to 3 visual analogue scale (VAS) at Screening.
12. Participants with concurrent diagnosis of fibromyalgia must have either positive anti-dsDNA or low C3 or C4 during screening or must be on immunosuppressive treatment (excluding antimalarials) other than oral corticosteroids only.
13. Chest radiograph (obtained during Screening or within 12 weeks prior to signing of the informed consent) or a CT scan of the chest (within 12 weeks of signing the informed consent) which meets all of the following:
- (a) No evidence of current active infection (e.g., pneumonia, TB) or previous TB; and
  - (b) No evidence of malignancy or no radiological findings of pulmonary nodules suspicious for lung cancer (as per applicable guidance, e.g., ACR Lung-RADS v2022 <https://www.acr.org/-/media/ACR/Files/RADS/Lung-RADS/Lung-RADS-2022.pdf>) without appropriate follow up prior to enrolment; and
  - (c) No clinically significant abnormalities (unless due to SLE).
14. Meets all of the following TB criteria:
- (a) No medical history or signs or symptoms of active TB prior to or during any Screening visit.
  - (b) A chest radiograph during the Screening Period or within 12 weeks prior to signing of the informed consent with no evidence of active or signs of prior TB infection.
  - (c) No recent contact with a person with active TB OR if there has been such contact, referral to a physician specializing in TB to undergo additional evaluation prior to randomisation (documented comprehensively in source), and, if warranted, receipt of appropriate treatment for latent TB initiated before the first administration of IMP.
  - (d) No history of latent TB prior to initial Screening visit, with the exception of latent TB with documented completion of appropriate treatment.

#### Testing for Inclusion in the Study:

The participant must undergo an Interferon gamma (IFN- $\gamma$ ) release assay (IGRA) (e.g., QuantiFERON-TB Gold [QFT-G] test) test for TB obtained from the study Central Laboratory at screening with any of the following results:

- (a) Negative test result.
- (b) Positive test result: referral to a TB specialist for evaluation and for which active TB has been ruled out (as described in the protocol definition), and initiation of treatment for latent TB prior to the first administration of IMP in accordance with local standard of care.
- (c) Indeterminate test result confirmed by repeat test using the same assay.
  - If in an endemic region\*, the participant must be referred to a TB specialist for evaluation (with assessment and treatment recommendation comprehensively documented in source) and initiation of appropriate latent TB treatment, if warranted, prior to the first administration of IMP. If no latent TB treatment is warranted, the participant may enter the study without latent TB treatment, but must be retested every 3 months for the first 6 months. If retest result at 6 months is indeterminate or negative, the participant may continue in the study without further testing.
  - If in a non-endemic region, the participant may enter the study without referral to a TB-specialist and latent TB treatment, but must be administered a retest every 3 months for the first 6 months. If, upon retest by the end of the 6 months the result is indeterminate, the participant may continue in the study without treatment and with routine TB testing.

\*Endemic region as defined based on World Health Organization (WHO) lists of High Burden Countries (HBC) for TB and multi-resistant (MDR) TB.

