### **5.2.6.2 Tuberculosis results from screening evaluations**

The procedures, and guidance for the evaluation of tuberculosis test results which must be performed based on the screening IGRA (i.e., QFT-G) test can be found in Section 3.1, Inclusion Criterion # 14.

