### **5.2.6.3 Tuberculosis monitoring during the study**

All participants will be monitored for signs and symptoms of TB over the course of the treatment Period and at the follow up visits using the standardized New or Reactivated TB Surveillance Questionnaire. This questionnaire must be completed at every onsite visit prior to receiving study intervention. If a participant presents with signs/symptoms of TB or positive findings on the routine questionnaire, an IGRA TB (QFT-G) test should be administered.

**Participants, with indeterminate QFT-G results** for both the initial and retest **at Screening and for whom latent TB treatment is not warranted**, must undergo repeat retesting every 3 months for 6 months see study plan (Section 4.1).

- If the retest QFT-G result is still indeterminate at Week 24, no further retesting is required until the Week 52 QFT-G required for all participants.
- Positive QFT-G test result, the participant should be referred to a TB specialist. If a TB specialist is not available, the local country guidelines should be followed for further diagnostic work up and anti-TB treatment regimens. If no local guidelines exist for immunocompromised individuals, then USA guidelines may be followed. This should also be reported as an AESI.
- Negative QFT-G test result, then the participant does not need to continue TB testing outlined for participants with indeterminate results at screening.

All participants must undergo QFT-G testing from the central laboratory for TB at Week 52. For participants with negative QFT at baseline and no symptoms of active TB:

- Week 52 QFT-G negative: no further testing.
- Week 52 QFT-G indeterminate: repeat at Week 56. If negative no further testing, however if indeterminate repeat again at Week 60.
- Week 52 QFT-G positive: repeat QFT-G test as soon as possible. If confirmed follow recommendations for positive QFT-G results during study. If repeat test is indeterminate or negative follow recommendation for indeterminate results above. Consider referral to TB specialist.

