### 6.3.5 Tuberculosis including latent tuberculosis

Tuberculosis (TB) is a mycobacterial infectious disease generally presenting as cough with systemic symptoms of infection diagnosed by skin test (purified protein derivative), blood test (IGRA), radiographic imaging, body fluid and tissue sampling; presentation may include disseminated or latent disease. An infection may be new (including conversion of a TB test to positive) or reactivation of dormant disease (new active disease in a previously TB test positive participant without prior evidence of active disease).

- **A bacteriologically confirmed TB case** is one where a biological specimen is positive by smear microscopy, culture or rapid diagnostic such as PCR or nucleic acid amplification test (Xpert MTB/RIF).
- **A clinically diagnosed TB case** is one that does not fulfil the criteria for bacteriological confirmation but has been diagnosed as active TB by a clinician or other medical practitioner who has decided to give the participant a full course of TB treatment. This definition includes cases diagnosed on the basis of radiograph abnormalities or suggestive histology and extra-pulmonary cases without laboratory confirmation. Clinically diagnosed cases subsequently found to be bacteriologically positive (before or after starting treatment) should be reclassified as bacteriologically confirmed.

Bacteriologically confirmed or clinically diagnosed cases of TB are also classified according to: anatomical site of disease; history of previous treatment; drug resistance; HIV status ([World Health Organization, 2014](#) and [2020](#)).

Latent TB is a mycobacterial infection without clinical, bacteriological, or radiologic findings consistent with active TB, but results in a positive TB blood test such as an IGRA (QuantiFERON-TB Gold). All participants must undergo IGRA[QFT-G] testing from the Central Laboratory for TB at screening and every 12 months through the duration of study (including the treatment and follow-up period) for both TB endemic and non-endemic regions as identified by the WHO ([World Health Organization, 2020](#)). Participants with a positive TB

blood test result, but no accompanying clinical or radiological work up should not be classified as having latent TB, but should be reported as being IGRA [QFT-G] test positive.

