Participants should be monitored and a standardized TB questionnaire conducted at each required visit according to study plan. If a participant presents with signs/symptoms of TB or positive findings in the routine questionnaire, an IGRA [QFT-G] TB test should be administered.

The following guidelines must be followed based on TB test results:

- Participants with a negative IGRA [QFT-G] test result must be tested for TB again every 12 months from randomisation in both endemic and non-endemic regions.
- Participants testing positive at any time for TB must be referred to a TB specialist for evaluation. Active TB must be ruled out and initiation of treatment for latent TB prior to the first administration of study intervention in accordance with local standard of care.
- If a participant has an indeterminate IGRA [QFT-G] test result, he/she must be retested immediately using the same assay
  - (a) If in an endemic region\*, and the results upon immediate retest remain indeterminate, the participant must be referred to a TB specialist for evaluation (with assessment and treatment recommendation properly documented in source) before any further IMP administration. If warranted, appropriate latent TB treatment must be initiated prior to continued administration of IMP. If no latent TB treatment is warranted, the participant may continue to receive IMP without latent TB treatment, but must be administered a retest every 3 months for 6 months. If upon retest by the end of the 6 months, the result is indeterminate, the participant may continue in the study without latent TB treatment and continue with routine TB testing.
  - (b) If in a non-endemic region, and the results upon immediate retest remain indeterminate, the participant may continue in the study without latent TB treatment, but must be administered a retest every 3 months for 6 months. If, upon retest by the end of the 6 months, the result is indeterminate, the participant may continue in the study without treatment.

\* Endemic region as defined based on WHO lists of High Burden Countries (HBC) for TB and multi-resistant (MDR) TB. (See current list, [World Health Organization](#), 2020).

NOTE:

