4.7 China Subpopulation Analyses

Approximately 80% of the participants are estimated to be recruited from mainland China. The efficacy and safety in China subpopulation (defined as all participants from sites in mainland China) were analyzed to facilitate a benefit-risk assessment for regulatory submission in China.

Efficacy are summarised for the China subpopulation, which consists of all randomized participants from sites in mainland China in the Full Analysis Set as defined in Section 3.2.2. Selected key analyses will be conducted and stratified analyses will not include the stratification factor region for the China subpopulation. These analyses are considered descriptive/supportive only, therefore no significance testing will be performed.

Safety and tolerability are summarised for the China subpopulation, which consists of all dosed participants from sites in mainland China in the Safety Analysis Set as defined in Section 3.2.3.

The PK data is summarised for the China subpopulation, which consists of all dosed participants from sites in mainland China in the Pharmacokinetic Analysis Set as defined in Section 3.2.4.

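### The protocol contradicts itself on TB blood testing after Month 6 for untreated participants with a confirmed indeterminate screening QFT-G, so a site could omit the scheduled Week 52 test

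*Protocol*

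**What the plan says.** The participants concerned have an indeterminate QFT-G at screening, confirmed by repeat, and no latent-TB treatment. All the TB sections have them retested every 3 months for 6 months; Table 4 footnote d places these retests at Weeks 12 and 24. The texts differ on what follows.

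- **Protocol 3.1, Inclusion 14(c), endemic region:** "If retest result at 6 months is indeterminate or negative, the participant may continue in the study without further testing".
- **Protocol 3.1, Inclusion 14(c), non-endemic region:** after an indeterminate result at 6 months, "the participant may continue in the study without treatment and with routine TB testing".
- **Protocol 6.3.5(a), endemic region:** after an indeterminate result at 6 months, "the participant may continue in the study without latent TB treatment and continue with routine TB testing".
- **Protocol 6.3.5(b), non-endemic region:** if "the result is indeterminate, the participant may continue in the study without treatment"; further testing is not mentioned.
- **Protocol 6.3.5, general rule:** "All participants must undergo IGRA[QFT-G] testing from the Central Laboratory for TB at screening and every 12 months through the duration of study", in both types of region. A separate bullet repeats the 12-monthly requirement for participants with a negative result.
- **Protocol 5.2.6.3:** a participant still indeterminate at Week 24 needs no retest before Week 52, and then "All participants must undergo QFT-G testing from the central laboratory for TB at Week 52". Region plays no part.
- **Protocol Table 4:** the TB blood test is marked at Week 52 and at the early discontinuation visit without restriction. Only the Week 12 and Week 24 marks carry footnote d.

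The cross-references also diverge. Section 5.2.6.2 says that guidance on results of the screening test "can be found in Section 3.1, Inclusion Criterion # 14". Table 4 footnote d sends the reader to Section 6.3.5 for the same participants.

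**The concern.** The same participant has no TB blood test after Week 24 under one text and a compulsory one at Week 52 under the others. Inclusion 14(c) and the branches of Section 6.3.5 also assign continued testing to opposite regions, so this is more than loose phrasing. The protocol does not say which section takes precedence.

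What is at stake is safety monitoring. Section 6.3 lists tuberculosis, including latent tuberculosis, as an adverse event of special interest, and SAP Section 4.6.2.2 tabulates it by treatment group. Section 6.3.5 describes latent TB as infection with a positive blood test and no clinical, bacteriological or radiological signs of active disease. A symptom questionnaire therefore cannot stand in for the test in detecting it. Participants who stay indeterminate also have no interpretable baseline result.

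**Working it through.** No figure in the plan bears on this point, so the check is a comparison of the texts. The rows below cross region with the Month 6 result, for untreated participants with a confirmed indeterminate screening result.

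| Region, Month 6 result | Inclusion 14(c) | 6.3.5 branch (a) or (b) | 6.3.5 general rules | 5.2.6.3 | Table 4 |
|---|---|---|---|---|---|
| Endemic, indeterminate | Testing ends | Routine testing goes on | Every 12 months, all participants | Pause, then Week 52 | Week 52 |
| Endemic, negative | Testing ends | Silent | Every 12 months, with negatives named | Extra series ends; Week 52 for all | Week 52 |
| Non-endemic, indeterminate | Routine testing goes on | Silent on testing | Every 12 months, all participants | Pause, then Week 52 | Week 52 |
| Non-endemic, negative | Silent | Silent | Every 12 months, with negatives named | Extra series ends; Week 52 for all | Week 52 |

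Reading across the rows:

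1. In both endemic rows Inclusion 14(c) stands alone against every other text that speaks. The negative row matters as much as the indeterminate one, because Section 6.3.5 names negatives explicitly.
2. In the non-endemic rows nothing conflicts. The silence of 6.3.5(b) is covered by the general 12-monthly rule of the same section.
3. The conflict with Section 5.2.6.3 is confined to Week 52, since that section itself allows a gap after Week 24.

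For an endemic-region participant who stays indeterminate, the QFT-G time points are:

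- Inclusion 14(c) taken literally: screening with its confirmatory repeat, Week 12, Week 24.
- Sections 5.2.6.3 and 6.3.5 and Table 4: the same, plus Week 52.

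The difference is one test, at Week 52.

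**The case against.** The best defence is that the texts can be read together. Inclusion 14(c) is permissive and comes straight after the description of the 3-monthly series, so the testing it ends may be only that series. Section 5.2.6.3 addresses this very group, keeps Week 52 for them, and uses mandatory language, as does the general rule in 6.3.5. The visit schedule marks the test. One can add that the branches in 6.3.5 are phrased around continuing study drug and so may be aimed at results arising on study, although footnote d sends screening-indeterminate participants there.

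Much of this stands, and it is why the missed test is only a risk. It does not dispose of the contradiction. Within one criterion, Inclusion 14(c) sets an endemic branch without further testing against a non-endemic branch with routine testing. If only the extra series were meant, that contrast would have no purpose. Section 5.2.6.3 states its limit expressly; Inclusion 14(c) does not.

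A reader might be tempted to infer more than the documents support:

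- **That sites are directed to the version that stops testing.** Section 5.2.6.2 covers results of the screening test only. On-study monitoring has its own section, and footnote d points to 6.3.5.
- **That the highest-risk group loses its test.** The protocol defines endemic regions by WHO lists but does not rank risk. Endemic-region participants go untreated only after a TB specialist finds treatment unwarranted.
- **That conversions would be missed.** Questionnaires continue at every visit, and symptoms or positive answers trigger a QFT-G. Only an asymptomatic conversion after Week 24 is exposed, and only if a site skips a scheduled test.
- **That most of those affected fall in the endemic branch.** SAP 4.7 says "Approximately 80% of the participants are estimated to be recruited from mainland China", but neither document states whether mainland China counts as endemic.

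**Conclusion.** The inconsistency is real and minor. It concerns whether the Week 52 QFT-G applies to endemic-region participants with a confirmed indeterminate screening result, no latent-TB treatment, and an indeterminate or negative result at Month 6. The consequence depends on a site following Inclusion 14(c) literally over Section 5.2.6.3, Section 6.3.5 and Table 4. In that case an asymptomatic conversion after Week 24 might not be captured as an adverse event of special interest. The last dose is at Week 48, so the Week 52 result bears on safety capture and not on dosing within the study.

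The number of participants concerned is not stated and cannot be derived from the documents. There is no effect on the primary analysis, the other efficacy analyses or the sample size.

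**What to change.** Reconcile Inclusion Criterion 14(c), Section 5.2.6.3 and Section 6.3.5 to a single text. It should say, for each type of region and for both an indeterminate and a negative Month 6 result, what testing follows and whether the Week 52 QFT-G applies. Make the pointers in Section 5.2.6.2 and Table 4 footnote d lead to that text. The clinical team decides the rule.

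The cost is wording in three sections and two cross-references. The Week 52 test is already in Table 4 for all participants, so keeping it there adds no procedure. If the clinical team decides otherwise, Table 4 needs a matching restriction.
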